1.6 Duration per participant

Main study: Up to 12 months of scheduled visits.

Extended follow-up: For the small group of participants with unresolved study product-related urticaria-associated symptoms (eg; wheal and flare lesions, pruritis, and/or erythematous lesions), up to an additional 48 months of scheduled contacts.

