8.5.2 Leukapheresis

Collection of PBMC via leukapheresis will be performed in accordance with the standard practices of the participating apheresis center. Ideally, in this procedure, approximately 1.5 liters of blood will be processed over about 1 hour using

peripheral veins for venous access. The blood will be anti-coagulated in accordance with standard practice of the apheresis center.

Post-procedural safety assessments will be performed in accordance with the standard practices of the participating apheresis center. Additionally, the participant will be advised to contact the study site if they experience any adverse events following the procedure.

Eligibility for leukapheresis:

- Prior to leukapheresis, participant must meet all apheresis center requirements for this procedure.
- Participants who can become pregnant must have a negative pregnancy test within 48 hours prior to the procedure.

8.6 Extended follow-up for participants with unresolved study product-related urticaria-associated symptoms

Participants with unresolved study product-related urticaria-associated symptoms (eg; wheal and flare lesions, pruritis, and/or erythematous lesions) at Visit 15 (month 12) will be asked to have follow-up remote contacts (eg, via phone) with CRS staff until all associated signs and symptoms resolve, or for up to an additional 48 months (4 years) after the month 12 visit, whichever time is shorter (see HVTN 302 SSP for detail). In addition, participants will come into the clinic for serum collections for banking at the following times (See [Appendix C](#)):

- Visit 102
- At clinic visit(s) scheduled in response to a urticaria-associated symptom. This can be multiple visits for a single flare or during recurrent visits for multiple flares.
- Participant's exit visit

A sample addendum informed consent form is provided in [Appendix G](#). Participants who consent for this extended follow-up period will follow the schedule of visits and evaluations shown in [Appendix C](#).

CRS staff will record the following:

- Updates on dermatological AEs deemed related to study product;
- New or updates to current concomitant medications;
- A brief urticaria-related symptom questionnaire;

- New SAEs, regardless of attribution to study product;
- New dermatological AEs, regardless of attribution to study product; and
- Targeted physical exam findings (if a physical exam is conducted).

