Serum for storage and assays ⁴	SST	0	17	As clinically indicated and at the participant's exit visit ⁴				17	17
Daily volume total (mL)	0	17	0	0	0	0	0	17	17
56-day total volume (mL)	0	17	0	0	0	0	0	17	

¹ **Medical history:** Based on the responses on urticaria-related symptom questionnaire, an interim medical history may be performed and documented in the participant's chart.

² **Concomitant medications**, including review of prescription and non-prescription drugs, vitamins, topical products, alternative/complementary medicines, recreational drugs, vaccinations, and allergy shots are updated and any new information is recorded at each contact.

³ Site may ask the participant to come in for a targeted (abbreviated) **physical exam** if during the remote visit, the participant reports anything that may require further evaluation. See Section 8.6.

⁴See Section 8.6. Participants in extended follow will have clinic visits to collect 17 mls serum for banking at Visit 102, their exit visit, and at any clinic visit(s) scheduled to further evaluate urticaria-associated symptoms.

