10.2 Analyses to investigate related urticaria adverse events

The following analyses will be conducted to generate potential explanations of the related urticaria adverse events observed in HVTN 302.

Urticaria cases are defined as participants who report any adverse event of urticaria (medDRA preferred term) of any duration deemed related to study product. Urticaria non-cases are defined as participants who do not report any such event.

Differences in baseline variables identified by the HVTN 302 protocol team leadership will be formally compared between urticaria cases and non-cases by Barnard's exact test for the following 15 binary variables at enrollment: female sex at birth, Hispanic or Latino ethnicity, race = White given data sparsity, history of eczema, history of seasonal and environmental allergies, history of food allergies, history of drug allergies, history of other and non-specified allergies, and use of antihistamine/asthma inhaler/steroid medications, COVID-19 infection, mRNA COVID-19 vaccination (Moderna or Pfizer), any Moderna COVID-19 vaccination, any Pfizer COVID-19 vaccination, Moderna received as last COVID-19 vaccination, Pfizer received as last COVID-19 vaccination. The Wilcoxon rank sum test will be used to evaluate differences in distribution of age in years at enrollment between urticaria cases and non-cases. Multiplicity adjustment of the p-values for comparing each of these 16 demographic characteristics and prior histories between participants with and without urticaria will be done to control the family-wise error rate at 0.05 using Holm, 1979 adjustment. For covariates where the unadjusted p-value was less than 0.05 for the association with urticaria, odds ratios (OR) and nominal 95% CIs were calculated by median-unbiased estimation (mid-p) method [1] with Haldane-Anscombe correction for 0 counts [2].

Tables

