- Demographics (sex at birth, ethnicity, race, age in years), prior conditions and use of allergy medications (history of eczema, history of seasonal and environmental allergies, history of food allergies, history of drug allergies, history of other and non-specified allergies, use of antihistamine/asthma inhaler/steroid medications at enrollment), Covid-19 infection prior to enrollment, receipt of any Covid-19 mRNA vaccination prior to enrollment, receipt of any Moderna Covid-19 mRNA vaccination prior to enrollment, receipt of Moderna as last Covid-19 mRNA vaccination prior to enrollment. Stratified by urticaria case/non-case status, summarized by n/N, % for binary/categorical variables and by 25%, median, 75% for age in years.
- Covid-19 vaccination post-enrollment stratified by urticaria case/non-case status, summarized by n/N (%).

Figures

- Timeline of vaccination times (grey open circles), blood draws (red points), and urticaria AE onset and resolution (salmon line segments or arrows if no resolution) for urticaria cases where x-axis denotes study weeks from enrollment and y-axis denotes ptid (study group).
- Boxplots of days from last mRNA Covid-19 vaccination to enrollment for urticaria cases and non-cases, with different point types denoting Pfizer (triangle) vs. Moderna (filled circle) vaccine.
- Boxplots of days from last Moderna Covid-19 vaccination to enrollment for urticaria cases and non-cases.
- Spaghetti plots of eosinophil and basophil counts over time with red lines denoting urticaria cases and grey dashed lines indicating non-cases.

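### The SAP 10.2 table of COVID-19 vaccination after enrolment by urticaria case status has no limit relative to onset and no data cut, so it cannot be read for or against vaccination as an explanation of onset

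*SAP*

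**What the plan says.** SAP Section 10.2 opens with its purpose: "The following analyses will be conducted to generate potential explanations of the related urticaria adverse events observed in HVTN 302". Case status has no onset window: "Urticaria cases are defined as participants who report any adverse event of urticaria (medDRA preferred term) of any duration deemed related to study product".

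The formal comparisons (Barnard and Wilcoxon tests with Holm adjustment) cover age and a set of binary characteristics, introduced as "for the following 15 binary variables at enrollment". COVID-19 vaccination after enrolment is not among them. It appears only as a descriptive table: "Covid-19 vaccination post-enrollment stratified by urticaria case/non-case status, summarized by n/N", with a percentage. No end date, data cut or limit relative to onset is given.

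Follow-up differs between participants. Protocol Section 1.6 gives "Main study: Up to 12 months of scheduled visits" for everyone. For a small group with persisting urticaria-type symptoms it adds "up to an additional 48 months of scheduled contacts". Under Protocol Section 8.6, participants whose product-related symptoms are unresolved "at Visit 15 (month 12) will be asked to have follow-up remote contacts", subject to consent. In Appendix C, footnote 2, concomitant medications in that period include "recreational drugs, vaccinations, and allergy shots are updated and any new information is recorded at each contact". The SAP does not mention the extended follow-up.

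The one display in SAP 10.2 that states it shows onset times is the timeline figure. It covers cases only and does not say whether its vaccination marks include COVID-19 vaccinations.

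**The concern.** A vaccination given after urticaria has begun cannot have caused that onset, and the onset may itself change whether and when it is given. A participant with hives may put off a COVID-19 vaccine. One who has stopped study vaccine no longer has to space COVID-19 vaccination around study doses. Pooling vaccinations before and after onset can therefore move the percentage in cases either way, for reasons unrelated to what started the events.

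Recording time is a second, conditional problem. If the table drew on extended follow-up, a subset rich in cases would have up to five times as long as others to accumulate a recorded vaccination.

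What is at stake is interpretation. A gap between cases and non-cases could be taken as a lead, or the absence of one as reassurance, when the table supports neither.

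**Working it through.** **1. Durations.** Per participant: 12 + 48 = 60 months, matching Visit 108 in Appendix C (Month 60, Day 260 × 7 + 1 = 1821). Whole study: 22 + 48 = 70 months, as stated in Protocol Section 1.7.

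**2. Share of main-study time after onset.** Inputs: study doses at Days 1, 57 and 169 and final visit at Day 365 (Appendices A and B). The assumed lag from dose to onset is 1 to 21 days, based on the range that Protocol Section 2.8 reports for COVID-19 vaccines; the documents give no lag for the study products. Formula: (365 − onset day) / 364.

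| Dose | Onset day | Share after onset |
|---|---|---|
| 1 | 2 to 22 | 363/364 to 343/364 = 99.7% to 94.2% |
| 2 | 58 to 78 | 307/364 to 287/364 = 84.3% to 78.8% |
| 3 | 170 to 190 | 195/364 to 175/364 = 53.6% to 48.1% |

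This uses no extended follow-up data.

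**3. Effect of vaccine spacing.** Protocol Section 5.2.1 requires 4 weeks between a SARS-CoV-2 vaccination and the next study dose, and recommends 4 weeks after a study dose. At target dates, the slot between doses 1 and 2 is Day 1 + 28 = 29 to Day 57 − 28 = 29, a single day. Between doses 2 and 3 it is Day 57 + 28 = 85 to Day 169 − 28 = 141. If the recommendation is followed, a dose 1 event with onset by Day 22 can have no earlier COVID-19 vaccination since enrolment. Every one counted for that participant would come after onset.

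**4. Unequal recording time, if extended follow-up were included.** Assume the same constant COVID-19 vaccination rate h in cases and non-cases, so there is no true association. Let f be the share of cases followed to Month 60; all others stop at Month 12. The documents give neither h nor f.

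- Non-cases: 1 − exp(−h)
- Cases: (1 − f)(1 − exp(−h)) + f(1 − exp(−5h))

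At h = 0.3 per year, 1 − exp(−0.3) = 25.9% and 1 − exp(−1.5) = 77.7%.

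| f | Non-cases | Cases | Gap (points) | Odds ratio |
|---|---|---|---|---|
| 0 (Month 12 cut) | 25.9% | 25.9% | 0 | 1.00 |
| 0.25 | 25.9% | 38.9% | 13.0 | 1.82 |
| 0.5 | 25.9% | 51.8% | 25.9 | 3.07 |
| 1.0 | 25.9% | 77.7% | 51.8 | 9.95 |

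Over h = 0.1 to 1.0 per year, the gap is about 7 to 13 points at f = 0.25 and about 15 to 26 at f = 0.5.

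**5. Equal windows remove the artefact.** At h = 0.3, both groups show 1.7% if cut at Day 22 and 14.4% if cut at Day 190, against 25.8% over the uncut main study (364 days). Truncating cases alone would bias the comparison the other way. A single median cut for non-cases is not enough either. Suppose three quarters of onsets fall on Day 22 and one quarter on Day 190. Cases then show 0.75 × 1.7 + 0.25 × 14.4 = 4.9%, while non-cases cut at the median (Day 22) show 1.7%. These percentages ignore the spacing in step 3, so the early ones are probably too high.

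**The case against.** The strongest reply is that this is one untested descriptive row in an exploratory section. It gets no p-value or odds ratio, it lies outside the Holm family, and the SAP makes no causal claim from it. Vaccination after onset is also not useless information, because it could bear on persistence or recurrence, which the section and the extended follow-up both address. All of this stands. It limits the importance of the point and argues for showing vaccinations after onset separately rather than discarding them.

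A reader might infer more than the documents support:

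- **That the 48 extra months are counted.** The SAP does not say so. Its scope is the Safety Monitoring Board reports and the final safety report, and the protocol keeps the extension apart with its own schedule and windows. Inclusion could be inferred only from silence.
- **That only cases are followed longer.** Entry depends on unresolved urticaria-type symptoms at Month 12 plus consent. A case that has resolved by then is not followed further. A participant whose event is coded to another preferred term could be a non-case and still enter.
- **That the artefact exceeds 50 points.** That needs every case to enter the extension, stay to Month 60 and have all those data tabulated. Follow-up stops at resolution, so 60 months is a ceiling.

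None of this answers the point about onset, which remains with a strict Month 12 cut.

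**Conclusion.** The point holds in a limited form. As written, the table mixes COVID-19 vaccinations before and after urticaria onset, so its case and non-case percentages are not evidence for or against COVID-19 vaccination as an explanation of onset. Under the assumed lag, roughly half (dose 3) to nearly all (dose 1) of main-study time falls after onset. The share of vaccinations after onset depends on their timing, which the documents do not give.

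The recording-time bias is conditional. It is zero with a Month 12 cut, and about 13 or 26 points if extended data were used with a quarter or half of cases followed to Month 60. Those figures rest on an assumed constant 0.3 vaccinations per year and no true association.

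It would go too far to say that the table has no value or that the urticaria investigation is compromised. The formal comparisons use enrolment variables and are unaffected. This is a low-priority improvement.

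**What to change.** Amend the table description in SAP Section 10.2:

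- In cases, report COVID-19 vaccinations from enrolment to first related urticaria onset separately from those after onset.
- Give each non-case an index date, in days from enrolment, matched to the case onset times, and count vaccinations up to it. Do not use one median cut.
- Cap the comparison at Month 12 and state the data cut. Report any extended follow-up vaccinations separately and descriptively, without a non-case comparison.
- Mark COVID-19 vaccinations on the case timeline figure, with a symbol distinct from study doses.

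No new data are needed, since vaccinations are already recorded as concomitant medications and the timeline already uses onset dates. The cost is a few SAP sentences and modest programming, mainly for the matched index dates. The downside is that counts before onset may be very small because of the spacing in Protocol Section 5.2.1. The row may then say little, but it would show how few vaccinations could have preceded onset.

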11 SAFETY TABLES, PARTICIPANT LISTINGS, AND FIGURES

11.1 List of Tables

The following tables are included in the SMB reports and FSR for Safety:

- Enrollment Report
- Demographics and Vaccination Frequencies
- Overall Protocol Status
- Maximum Local and Systemic Reactogenicity Summaries
- Adverse Experiences by Body System and Severity – By Decreasing Frequency
- Adverse Experiences by Preferred Term and Severity – By Decreasing Frequency – Includes Severe, Life-threatening or Fatal Experiences Only
- Adverse Experiences by Preferred Term and Severity – By Decreasing Frequency – Includes Experiences of All Severities
- Adverse Experiences by Preferred Term and Relationship to Study Product – By Decreasing Frequency – Includes Related Experiences Only
- Adverse Experiences by Preferred Term and Relationship to Study Product – By Decreasing Frequency – Includes Experiences of Any Relationship
- Expedited Adverse Experiences (EAEs) Reported to the Regulatory Support Center (RSC)
- Pregnancy Listing

Additional tables included in the FSR for Safety:

- Social Impact Summary
- FNA/Leukapheresis Related Events
- Listing of Urticaria Adverse Events
- End of Study Diagnostic Testing Results for Vaccinees
- Local Lab Value Summary Statistics
- Local Laboratory Values Meeting Grade 1 AE Criteria or Above

11.2 List of Participant Listings

These participant listings are included in the SMB reports:

- Discontinuation Status
- Pregnancies
- Severe or Life-Threatening Local and Systemic Reactogenicities
- Moderate Erythema and Induration
- Expedited Adverse Experiences (EAEs)
- Adverse Experiences of Special Interest (AESIs)
- Severe, Life-Threatening, or Fatal Adverse Experiences
- Adverse Experiences with Relationship to Study Product
- HIV Infection Results from Lab and Reported by Site

11.3 List of Figures

These graphs are included in the SMB reports and FSR for Safety:

- Maximum Local Reactogenicities
- Maximum Systemic Reactogenicities
- Boxplots for CBC, ALT, Creatinine, Hemoglobin, WBC, Platelets

